APPENDIX E. SUMMARY OF CHANGES

Previous Protocol Versions

Protocol	Date
Version 1.0	11 December 2020
Administrative Change 1	24 March 2021

The purpose of this version is to update the following sections and incorporate necessary protocol modifications due to the COVID-19 pandemic and changes due to new safety information available as follows:

Modifications to the Protocol and Operations Manual due to State-of-Emergency or Pandemic Situations

- Vaccine language was updated. A COVID-19 vaccine eCRF is being implemented in the study.
 - Sections affected include: Protocol Section 5.4, Operations Manual Section 4.3

Rationale: To ensure subject safety during state-of-emergency or pandemic situations.

 In Section 2.1 of the Operations Manual, the activities list was updated to indicate that Week 16 labs may be processed at a local lab, if needed.

Rationale: Vendor kit shortages due to the COVID-19 pandemic may necessitate the use of local labs.

• In Section 3.12 of the Operations Manual, language was provided regarding acceptable modifications to ECG collection.

Rationale: Due to protocol modifications in state of emergency or pandemic situations, acceptable alternatives may need to be employed.

Protocol

- Text was updated throughout the Protocol to align with revisions in the protocol template and changes due to new safety information available.
 - Sections include: Section 5.1, Section 5.2, Section 5.4, Section 5.5, Section 6.1 (Table 3), Appendix D (Activity Schedule)

Rationale: Updated language to provide align with new safety information available and provide additional clarity.

• Throughout the Protocol, made typographical, stylistic, and administrative updates.

Rationale: To correct known typographical, stylistic, and administrative inconsistencies.

Operations Manual

- Text was updated throughout the Operations Manual to align with revisions in the Operations Manual template and changes due to new safety information available.
 - Sections include: Section 3.12, Section 3.16, Section 4.1

Rationale: Updated language to provide align with new safety information available and provide additional clarity.

• Protocol Section 2.1 was updated to clarify that vital signs, height, weight, and PASI would not be collected at virtual visits, if utilized (Week 4, Week 28, Week 40, and Week 52). Hematology and clinical chemistry labs at Week 16 were updated with a "+" to indicate that these labs could be performed locally, if needed.

Rationale: To provide clarity and correct the discrepancy between the text and visit activities lists. Vendor kit shortages may result in the need to use local laboratories.

• Throughout the Operations manual, made typographical, stylistic, and administrative updates. *Rationale:* To correct known typographical, stylistic, and administrative inconsistencies.

1.0 Introduction

This Statistical Analysis Plan (SAP) describes the statistical analyses for risankizumab Study M15-994, A Phase 3b Multicenter, Randomized, Double-Blind, Parallel-Group, Placebo-Controlled Study Evaluating Safety and Efficacy of Risankizumab Compared to Placebo in Adult Subjects with Moderate to Severe Plaque Psoriasis with Palmoplantar (Non-Pustular) Involvement (PPPsO).

Study M15-994 assesses the safety and efficacy of risankizumab (150 mg) versus placebo for the treatment of signs and symptoms of moderate to severe plaque psoriasis in patients with (non-pustular) palmoplantar involvement.

This SAP provides summaries of the planned statistical analyses for safety and efficacy endpoints, and overall type-I error control strategies.

The SAP will not be updated in case of administrative changes or amendments to the protocol unless the changes impact the analysis.

Unless noted otherwise, all analyses will be performed using SAS Version 9.4 (SAS Institute Inc., Cary, NC 27513) or later under the UNIX operating system.

2.0 Study Design and Objectives

2.1 Objectives, Hypotheses and Estimands

The primary objective of this study is to assess the safety and efficacy of risankizumab (150 mg) versus placebo for the treatment of signs and symptoms of moderate to severe plaque psoriasis in patients with (non-pustular) palmoplantar involvement.

Primary Efficacy

The primary efficacy objective is to demonstrate a higher rate of Palmoplantar Investigator's Global Assessment (ppIGA) of "clear" or "almost clear" (0 or 1) with at least a 2-point reduction from Baseline at Week 16 of treatment with risankizumab

(150 mg) compared to placebo in the Intent-to-Treat (ITT) Population, which consists of all randomized subjects (Section 5.0).

The hypothesis corresponding to the primary endpoint is:

- The proportion of subjects achieving ppIGA of 0 or 1 with at least a 2-point reduction from Baseline with risankizumab is greater than that with placebo at Week 16.

The estimand corresponding to the primary endpoint is defined using composite variable strategy:

- Difference in the proportion of subjects achieving ppIGA of 0 or 1 with at least a 2-point reduction from Baseline at Week 16 without premature discontinuation of study drug due to lack of efficacy prior to Week 16, in the risankizumab group in comparison with the placebo group in the ITT population.

Secondary Efficacy

The secondary efficacy objectives are based on the ranked secondary endpoints as defined in Section 3.2. The hypotheses and estimands corresponding to these ranked secondary endpoints are summarized in Table 1.

Table 1. Hypotheses and Estimands Corresponding to the Ranked Secondary Endpoints

Hypothesis	Estimand
1. The proportion of subjects achieving PPASI 75 with risankizumab is greater than that with placebo at Week 16.	Difference in the proportion of subjects achieving PPASI 75 at Week 16 without premature discontinuation of study drug due to lack of efficacy prior to Week 16 in the risankizumab group in comparison with the placebo group in the ITT population.
2. The proportion of subjects achieving PPASI 90 with risankizumab is greater than that with placebo at Week 16.	Difference in the proportion of subjects achieving PPASI 90 at Week 16 without premature discontinuation of study drug due to lack of efficacy prior to Week 16 in the risankizumab group in comparison with the placebo group in the ITT population.
3. The proportion of subjects achieving sPGA of 0 or 1 with at least a 2-point reduction from Baseline with risankizumab is greater than that with placebo at Week 16.	Difference in proportion of subjects achieving sPGA of 0 or 1 with at least a 2-point reduction from Baseline at Week 16 without premature discontinuation of study drug due to lack of efficacy prior to Week 16 in the risankizumab group in comparison with the placebo group in the ITT population.
4. The proportion of subjects achieving PPASI 100 with risankizumab is greater than that with placebo at Week 16.	Difference in the proportion of subjects achieving PPASI 100 at Week 16 without premature discontinuation of study drug due to lack of efficacy prior to Week 16 in the risankizumab group in comparison with the placebo group in the ITT population.

ITT = intent-to-treat; PPASI = Palmoplantar Psoriasis Area and Severity Index; sPGA = static Physician's Global Assessment

2.2 Study Design Overview

This is a Phase 3b, multicenter, randomized, double-blind, parallel group, placebo-controlled study to evaluate the safety and efficacy of risankizumab (150 mg) compared to placebo in adult subjects with moderate to severe plaque psoriasis with palmoplantar involvement.

The study is comprised of a Screening period of up to 35 days, a 52-week treatment period, and a follow up phone call for safety.

[figure not shown]
The 52-week treatment period includes Period A and Period B.

- Period A, Double-Blind Period (Baseline to Week 16): Eligible subjects will be centrally randomized at the Baseline visit in a 1:1 ratio to receive either risankizumab 150 mg as a single subcutaneous (SC) injection, or matching placebo. Study drug administration will occur at Baseline and Week 4. The final efficacy evaluation of Period A will be at Week 16.
- Period B, Open-Label Period (Week 16 to Week 52): Starting at Week 16, all subjects will receive open label risankizumab 150 mg once every 12 weeks at Weeks 16, 28, and 40. The final efficacy evaluation of Period B will take place at Week 52.

A follow-up phone call for safety will be conducted approximately 20 weeks after administration of the last dose of risankizumab (e.g., Week 60).

The schematic of the study is shown in [Figure 1](#).

Figure 1. Study Schematic

Solid arrows indicate administration of study drug at study visits.

Wk = week.

The Primary Analysis will be performed after the last ongoing subject completing the Week 16 visit or permanently discontinuing the placebo-controlled period, and the data up to Week 16 cutoff date have been cleaned.

2.3 Treatment Assignment and Blinding

All subjects will be assigned a unique identification number by the interactive response technology (IRT) system at the screening visit. For subjects who rescreen, the screening number assigned by the IRT at the initial screening visit should be used. The IRT will assign a randomization number that will encode the subject's treatment group assignment according to the randomization schedule generated by Data and Statistical Sciences (DSS) at AbbVie.

Subjects will be centrally randomized at the Baseline visit in a 1:1 ratio to receive either SC risankizumab 150 mg or matching placebo during Period A, and all subjects will receive open label risankizumab 150 mg once every 12 weeks during Period B. Randomization will be stratified by Baseline ppIGA ("moderate" [3] versus "severe" [4]) and Baseline body surface area (BSA) affected (< 10% versus \geq 10%).

All AbbVie personnel with direct oversight of the conduct and management of the study (with the exception of AbbVie Drug Supply Management Team) will remain blinded until the Primary Analysis at Week 16 is available. The investigator, study site personnel, and the subject will remain blinded to each subject's treatment throughout the study. To maintain the blind, the risankizumab pre-filled syringe (PFS) and placebo PFS provided for the study will be identical in appearance.

In the event of a medical emergency in which the investigator believes that knowledge of study drug treatment is required, reasonable efforts must be made to contact the AbbVie emergency contact prior to breaking the blind, as long as it does not compromise subject safety. However, if an urgent therapeutic intervention is necessary which warrants breaking the blind prior to contacting the AbbVie emergency contact, the investigator can directly access the IRT system to break the blind without AbbVie agreement. The date

and reason that the blind was broken must be recorded in the source documentation and electronic case report form (eCRF), as applicable.

2.4 Sample Size Determination

The ppIGA is an endpoint that has been used in another clinical trial in the palmoplantar psoriasis population and which is based on the modified Investigator's Global Assessment version of 2011.^{1,2} Given the lack of historical ppIGA data from risankizumab trials, the assumption of response rates in the current study are based on the relevant endpoints of PPASI 75 and PPASI 90 from risankizumab PsO Studies M15-992, M15-995, and M16-008, among subjects who had Baseline PPASI of at least 8. Among these subjects, approximately 80% and 75% of subjects from the risankizumab (RZB) group achieved PPASI 75 and PPASI 90, respectively; compared to 50% and 40% in the placebo (PBO) group.

Assuming that 75% of subjects from the RZB group and 45% of subjects from the PBO group would achieve the primary endpoint of ppIGA of 0 or 1 with at least a 2-point reduction from Baseline at Week 16, the sample size of 168 subjects (84 subjects per group) will provide more than 90% power to detect the treatment difference between RZB and PBO, under a 2-sided significance level of 0.05.

3.0 Endpoints

3.1 Primary Endpoint

The primary endpoint is the achievement of ppIGA of 0 or 1 with at least a 2-point reduction from Baseline at Week 16.

3.2 Secondary Endpoint

The following ranked secondary endpoints will be tested in a hierarchical order, only if the null hypothesis for the primary endpoint has been rejected:

1. Achievement of PPASI 75 response at Week 16
2. Achievement of PPASI 90 response at Week 16
3. Achievement of sPGA of 0 or 1 with at least a 2-point reduction from Baseline at Week 16
4. Achievement of PPASI 100 response at Week 16

3.3 Additional Endpoints

All primary and ranked secondary endpoints will be analyzed at all other visits collected. In addition, the following endpoints will be analyzed at all visits collected:

- Achievement of ppIGA of "clear" (0)
- Achievement of sPGA of "clear" (0)
- Change from Baseline in PPASI
- Percent change from Baseline in PPASI
- Change from Baseline in PASI
- Percent change from Baseline in PASI among subjects with Baseline PASI ≥ 12
- Change and percentage change from Baseline in Patient Global Assessment of Skin Pain (PGA-SP), among subjects with Baseline PGA-SP NRS ≥ 4
- Change from Baseline in Psoriasis Symptom Scale (PSS)
- Achievement of PSS 0 or 1
- Change from Baseline in Dermatology Life Quality Index (DLQI)
- Achievement of DLQI 0 or 1
- Achievement of DLQI improvement (reduction) of ≥ 4 points, among subjects with Baseline DLQI ≥ 4

In addition, the achievement of ppIGA of "clear" (0), ppIGA of "clear" or "almost clear" (0 or 1) with at least a 2-point reduction from Baseline, and PPASI 75/90/100 response will also be summarized at later visits in Period B, among subjects who are randomized to risankizumab in Period A and have achieved the corresponding response status at the entry of Period B.

3.4 Safety Endpoints

The following safety evaluations will be performed throughout the study as measures of safety and tolerability:

- Adverse event (AE) monitoring
- Vital sign measurements
- Physical examinations
- Clinical laboratory testing

3.5 Pharmacokinetic Endpoints

No PK data will be collected for the purpose of PK analysis in present study.

4.0 Analysis Populations

The Intent-to-Treat (ITT) Population includes all randomized subjects. The ITT Population will be used for all efficacy analyses. Subjects who are randomized to placebo in Period A and do not continue into Period B will be excluded from the analysis in Period B.

The following populations will be used for the safety analysis:

- The Safety Population in Period A (Safety_A) is defined as all subjects who are randomized and received at least 1 dose of study drug in Period A.
- The Safety Population in Period B (Safety_B) is defined as all subjects who received at least 1 dose of study drug in Period B.

- The All Risankizumab Treated (ALL_RZB) Population is defined as subjects who received at least 1 study drug of risankizumab. This population will be used to provide a comprehensive summary of key safety variables.

5.0 Subject Disposition

A summary of subject accountability will be provided where the number of subjects in each of the following categories will be summarized by treatment groups:

- Subjects randomized in the study
- Subjects who received at least one dose of study drug in each Study Period
- Subjects who completed each Study Period
- Subjects who discontinued study drug in each Study Period (all reasons and primary reason)

For end of study participation, the number and percentage of subjects who did not complete each Study Period with associated reasons will be summarized overall and by treatment group.

6.0 Study Drug Duration and Compliance

For the Safety Populations in Period A and in Period B, the duration of treatment will be summarized by treatment groups. The duration of treatment for each period is defined as follows:

Period A: the minimum of (the last dose date in Period A + 84 days, the end of study date + 1 day, and the first dose date in Period B if not missing [and cutoff date during the Primary Analysis + 1 day]) minus the first dose date in Period A.

Period B: the minimum of (the last dose date in Period B + 84 days, and the end of study date + 1 day [and cutoff date during the Primary Analysis + 1 day]) minus the first dose date in Period B.

The duration of treatment will also be summarized among the ALL_RZB Population, which is defined as: the minimum of (the last dose date of risankizumab + 84 days, and the end of study date + 1 day [and cutoff date during the Primary Analysis + 1 day]) minus the first dose date of risankizumab.

Duration of treatment will be summarized by descriptive statistics of mean, standard deviation, median, minimum and maximum, among the number of subjects treated in each period.

Treatment compliance will be summarized by treatment groups among the Safety Populations in Period A and in Period B. The compliance will be summarized by the percentage of planned injections which are administered at each study drug administration visit. The cumulative summary of compliance in each period will also be provided. When computing the compliance at each study drug administration visit for each treatment group, the denominator will include all subjects in this treatment group who received at least one dose of study drug in the Study Period and have not prematurely discontinued the study drug prior to that scheduled visit.

7.0 Demographics, Baseline Characteristics, Medical History, and Prior/Concomitant Medications

7.1 Demographics and Baseline Characteristics

Continuous demographic variables include age, weight, height, and body mass index (BMI). Categorical demographic variables include sex, ethnicity, race, age (< 40 or ≥ 40 years), weight (≤ 100 or > 100 kg), BMI (< 25, ≥ 25 – < 30, ≥ 30 kg/m²), tobacco user (current, former, never, unknown), and alcohol user (current, former, never, unknown).

Baseline disease characteristics include history of psoriatic arthritis (yes, no), Baseline ppIGA categories, Baseline sPGA categories, Baseline BSA categories (< 10%, ≥ 10%), Baseline PASI, Baseline PPASI, Baseline BSA, Baseline PSS, Baseline PGA-SP, and Baseline DLQI.

Demographics and baseline disease characteristics will be summarized among the ITT Population, overall and by treatment groups. Categorical variables will be summarized with the number and percentage of subjects; percentages will be calculated based on the number of non-missing observations. Continuous variables will be summarized with descriptive statistics (number of non-missing observations, mean, standard deviation, median, minimum and maximum).

7.2 Medical History

Medical history data will be coded using the Medical Dictionary for Regulatory Activities (MedDRA). The actual version of the MedDRA coding dictionary will be noted in the statistical tables and clinical study report. The number and percentage of subjects in each medical history category (by MedDRA system organ class and preferred term) will be summarized overall and by treatment groups. The system organ class (SOC) will be presented in the alphabetical order, and the preferred terms will be presented in alphabetical order within each SOC. Subjects reporting more than one condition/diagnosis will be counted only once in each corresponding category (SOC or preferred term).

Medical history will be summarized among the ITT Population.

7.3 Prior and Concomitant Medications

Prior and concomitant medications will be summarized by generic names. A prior medication is defined as any medication taken prior to the first dose date of study drug. A concomitant medication is defined as any medication that is started prior to the first dose date of study drug and continued to be taken on or after the first dose date of study drug, or any medication that is started on or after the first dose date of study drug, but not after the last dose date of study drug plus 140 days. The number and percentage of subjects taking medications will be summarized by generic drug names based on the World Health Organization (WHO) Drug Dictionary for both prior and concomitant medications.

In addition, subjects' prior biologic therapy for psoriasis will also be summarized by the reason for discontinuation.

Prior and concomitant medications will be summarized among the ITT Population.

8.0 Handling of Potential Intercurrent Events for the Primary Endpoint and Key Secondary Endpoints

The primary efficacy endpoint (defined in Section 3.1) and four ranked secondary endpoints (defined in Section 3.2), will be analyzed in the ITT Population and the following method will be used to address the potential intercurrent event:

- Subjects who discontinue study drug due to lack of efficacy prior to Week 16 will be considered as non-responders at Week 16.

9.0 Efficacy Analyses

9.1 General Considerations

All efficacy analyses will be conducted among the ITT Population. All statistical tests will be performed at a 2-sided alpha level of 0.05.

The Primary Analysis will be conducted after all continuing subjects complete Week 16 and all data pertaining to Period A are cleaned. This will be the only and final analysis for efficacy in Period A. Study sites and subjects will remain blinded to their initial treatment assignment for the duration of the entire study.

For categorical endpoints, comparisons will be made between risankizumab and placebo using the Cochran-Mantel-Haenszel (CMH) test, adjusting for the actual values of stratification factors (Baseline ppIGA and Baseline BSA categories). In case of any stratum with zero subject in either treatment group, no stratification factor will be controlled. Non-responder imputation (NRI) incorporating multiple imputation (MI) to handle missing data due to COVID-19 (NRI-C) will be the primary approach to handle missing values.

For continuous endpoints, comparisons will be made between risankizumab and placebo based on the fixed term of treatment from a Mixed-effect Model Repeat Measurement (MMRM) model including the Baseline value and observed measurements at all post-baseline visits, adjusting for the fixed effects of treatment, actual values of stratification factors, visit and treatment-by-visit interaction as covariates. The MMRM will be the primary approach to handle missing values.

"Baseline" refers to the last non-missing observation on or before the date of the first administration of study drug or the date of randomization if no study drug is administered. For variables where the assessment time is collected on the ePRO device, the baseline measurement must be prior to the time of the first administration of study drug.

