5 STUDY ACTIVITIES

5.1 Eligibility Criteria

Subjects must meet all of the following criteria in order to be included in the study. Anything other than a positive response to the questions below will result in exclusion from study participation.

Consent

- 1. Subjects or their legally authorized representative must voluntarily sign and date an informed consent, approved by an independent ethics committee (IEC)/institutional review board (IRB), prior to the initiation of any screening or study-specific procedures.
- 2. Employees of the Sponsor and/or study sites and their family members may not be enrolled in this study.
- 3. Subjects must be willing and able to comply with procedures required in this protocol.

Demographic and Laboratory Assessments

- 4. Adult male or female, at least 18 years old (subjects must also meet the legal age of majority per local law).
- 5. Laboratory values meeting the following criteria within the Screening period prior to the first dose of study drug:
 - Serum aspartate aminotransaminase (AST) ≤ 2 × upper limit of normal (ULN);
 - Serum alanine aminotransaminase (ALT) ≤ 2 × ULN;
 - Serum total bilirubin ≤ 2.0 mg/dL; except for subjects with isolated elevation of indirect bilirubin relating to Gilbert syndrome;
 - Total white blood cell (WBC) count \geq 3,000/µL;
 - Absolute neutrophil count (ANC) \geq 1,500/µL;

- Platelet count \geq 100,000/µL;
- Hemoglobin \geq 10 g/dL (100 g/L).

Disease Activity

- 6. Female or male adults with chronic PPPsO (with or without psoriatic arthritis) for at least 6 months prior to Baseline and a ppIGA of "moderate" or "severe" (≥ 3), at Screening and Baseline.
- 7. Subjects must have at Screening and Baseline:
 - Plaque PsO BSA involvement of $\geq 1\%$,
 - sPGA score of "moderate" or "severe" (≥ 3),
 - PPASI \geq 8 (moderate or severe disease), and
 - At least 1 additional PsO plaque outside of the palms and soles.

At least 50% of the overall study population will be comprised of subjects with Baseline BSA \geq 10%.

- 8. Previously inadequately controlled disease by topicals, phototherapy, and/or systemic treatments.
- 9. Subject must be a candidate for systemic therapy as assessed by the investigator.

Subject History

- I0. Subject is judged to be in good general health, as determined by the investigator based upon the results of a medical history, physical examination, laboratory profile, and a 12-lead electrocardiogram (ECG) performed during the Screening period.

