9.6 Efficacy Subgroup Analyses

To evaluate the consistency of the efficacy over demographic and other baseline disease characteristics, the primary efficacy endpoint will be analyzed in selected subgroups as follows:

- Age group (< 40 years, ≥ 40)
- Sex (male, female)
- Race (white, non-white)

- Smoking (current, ex- or never)
- Body mass index (BMI) (normal: < 25, overweight: ≥ 25 to < 30, obese: ≥ 30)
- Baseline ppIGA ("moderate" [3], "severe" [4])
- Baseline BSA (< 10% versus ≥ 10%);
- Psoriatic arthritis (yes, no)
- Body weight (≤ 100 kg, > 100 kg)

Of note, if the BMI ≥ 30 subgroup have fewer than 10% of the total subjects, it will be combined with its adjacent subgroup.

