MODEL *//*OVERRIDE MISSING VALUES NOT DUE TO COVID-19 WITH TRADITIONAL
NRI*/
DATA ALLF; SET ALL;
  /*COVID19_XX='Y' IF MISSING AT WEEK XX IS DUE TO COVID-19; IF NOT,
OVERRIDE WITH TRADITIONAL NRI*/
  /*VARIABLE PPASI75NRI_XX: TRADITIONAL NRI DATA AT WEEK XX, WHICH
COVERS THE SPECIAL HANDLING SUCH AS THE BEFORE-AND-AFTER EXCEPTION IN
THE PARTICULAR STUDY PERIOD*/
  IF COVID19_16 NE 'Y' THEN PPASI75_16= PPASI75NRI_16;
RUN;
PROC SORT DATA=ALLF; BY _IMPUTATION_ SUBJID; RUN;

/*****
/*ANALYSIS MODEL*/
/*****

```

```
/*KEY CODE: ANALYZING EACH 'COMPLETE' DATASET*/  
/*****/  
/*INDIVIDUAL-LEVEL DATA --> # OF RESPONDERS & # OF SUBJECTS, TO BE READ-  
IN TO PROC STDRADE*/  
PROC FREQ DATA=ALL;  
  BY _IMPUTATION_;  
  TABLES TRT01PN*STRATAN* PPASI75_16/LIST NOCUM NOPRINT OUT=COUNT_TABLE;  
  /*WEEK 16 RESULTS AS AN EXAMPLE*/  
RUN;  
DATA COUNT_TABLE; SET COUNT_TABLE;  
  DROP PERCENT;  
RUN;  
PROC TRANSPOSE DATA=COUNT_TABLE OUT=FREQ_TABLE PREFIX=RESP;  
ID PPASI75_16;  
BY _IMPUTATION_ TRT01PN STRATAN;  
VAR COUNT;  
RUN;  
DATA FREQ_TABLE1; SET FREQ_TABLE;  
  CASE=RESP1;  
  SIZE=SUM(RESP0, RESP1);  
  KEEP _IMPUTATION_ TRT01PN STRATAN CASE SIZE;  
RUN;  
  
/*RE-ORDER TO SET 1 (PLACEBO) AS THE REFERENCE GROUP*/  
DATA FREQ_TABLE2; SET FREQ_TABLE1;  
  IF TRT01PN=2 THEN TRT01PN=0;  
RUN;  
  
/*CALCULATE THE COMMON RISK DIFF FOR EACH COMPLETE DATASET*/  
PROC STDRADE DATA=FREQ_TABLE2  
  METHOD=MH STAT=RISK EFFECT=DIFF;  
  BY _IMPUTATION_;  
  POPULATION GROUP=TRT01PN EVENT=CASE TOTAL=SIZE;  
  STRATA STRATAN / ORDER=DATA STATS(CL=NONE) EFFECT;  
  ODS OUTPUT EFFECT=EFFECT;  
RUN;  
  
/*COMBINING RESULTS USING PROC MIANALYZE*/  
/*****/  
PROC MIANALYZE DATA=EFFECT;  
  ODS OUTPUT PARAMETERESTIMATES=RISK_DIFF_MH;  
  MODELEFFECTS RiskDiff;  
  STDERR StdErr;  
RUN;
```

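### Does the empty-stratum fallback in SAP 9.1 discard a usable stratification factor in the ppIGA and BSA subgroups?

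*SAP*

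**What the plan says.** SAP 2.3 sets up four randomisation strata: "Randomization will be stratified by Baseline ppIGA" (moderate or severe) and by Baseline BSA (below 10%, or 10% and above). SAP 9.1, General Considerations, prescribes the CMH test with both factors for categorical endpoints, followed by the fallback: "In case of any stratum with zero subject in either treatment group, no stratification factor will be controlled". No intermediate step is given, such as keeping one factor or merging strata.

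SAP 9.6 says that "the primary efficacy endpoint will be analyzed in selected subgroups as follows", and its list includes Baseline ppIGA and Baseline BSA. The section repeats no test and gives no rule for sparse strata. Its only small-group rule concerns the BMI category of 30 and above. Protocol 7.4 lists the same subgroups and has no fallback.

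The sample code in SAP Appendix E, section 3.0, tabulates observed cells only ("TABLES TRT01PN*STRATAN* PPASI75_16/LIST NOCUM NOPRINT"). It is a whole-population example for PPASI 75, with no subgroup step and no empty-arm check.

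Protocol 7.7 and SAP 13.0 confine type I error control to the primary and ranked secondary endpoints.

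**The concern.** A stratum with no subject in one arm has Mantel-Haenszel weight zero, so the remaining strata can still be used. The SAP instead gives up all stratification for every subject, which looks like more than the method requires.

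The point is sharper in four subgroup levels. Within ppIGA moderate, for example, the two severe strata are empty by definition. Counted against the full set of four strata, the fallback applies every time and BSA is dropped although both its levels are present. Counting only observed strata keeps BSA. Two programmers could therefore report different p-values and intervals for the same subgroup.

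The rule could also apply in other small subgroups, and in the additional endpoint restricted at baseline ("Achievement of DLQI improvement (reduction) of ≥ 4 points, among subjects with Baseline DLQI ≥ 4"). At stake would be some precision, and reproducibility of the subgroup table.

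**Working it through.** **Inputs from the documents.** N = 168, 84 per arm, response 75% against 45%, two-sided 0.05 (SAP 2.4). Four strata (SAP 2.3). The BSA quota in Protocol 5.1 ("At least 50% of the overall study population will be comprised of subjects with Baseline BSA" of 10% or more) makes that subgroup at least 84 subjects, or 42 per arm.

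**Assumed, because the documents do not say.** Share with severe ppIGA 10% to 30%; BSA of 10% or more in 50% to 60%; block size; prognostic strength of the other factor.

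**1. The plan's own power figure.** Null SE = √(0.60 × 0.40 × 2/84) = 0.0756. Alternative SE = √((0.1875 + 0.2475)/84) = 0.0720. z = (0.30 − 1.96 × 0.0756)/0.0720 = 2.11, so power is 98.3%. The statement of more than 90% holds.

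**2. How often the full-population test meets the rule.** Simulated chance that at least one of the four strata lacks an arm, over 50% to 60% with BSA of 10% or more:

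| Severe ppIGA | Blocks of 4 | Blocks of 8 | Simple 1:1 |
|---|---|---|---|
| 10% | 0.8–1.8% | 1.8–3.3% | 5.6–7.7% |
| 20% | <0.01% | ≤0.02% | 0.1–0.2% |
| 30% | 0% | 0% | ≤0.01% |

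**3. Cost of the word-for-word reading in a ppIGA or BSA subgroup.** Take n = 84, split evenly on the other factor, with arms balanced within its levels by the stratified randomisation. Let placebo response be a and b in the two levels, averaging 45%.

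The unadjusted test assumes null variance 0.45 × 0.55 = 0.2475 per subject. The true within-level variance is v = [a(1−a) + b(1−b)]/2. Its actual size is 2 × [1 − Φ(1.96 × √(0.2475/v))].

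- 48/42%: v = 0.2466, size 5.0%.
- 55/35%: v = 0.2375, size 4.5%.
- 65/25%: v = 0.2075, size 3.2%.

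Size never exceeds 5%, because v cannot exceed 0.2475.

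Simulation with blocks of 4 and a 30-point effect in each level agrees:

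| Placebo response by level | Size, unadjusted / stratified | Power, unadjusted / stratified |
|---|---|---|
| 48/42% | 4.8 / 4.9% | 81.8 / 81.8% |
| 55/35% | 4.4 / 5.1% | 82.3 / 83.5% |
| 65/25% | 3.2 / 5.1% | 84.1 / 88.9% |

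Keeping the other factor gains 0, 1.2 and 4.8 points of power. A repeat run agreed within 0.3 points.

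**4. Would merging strata be better?** One alternative merges the two BSA strata within a ppIGA level, then merges across ppIGA. In simulated subgroups of 17 to 60 subjects where the rule applied, the size of the unadjusted fallback was 4.8–6.3% and that of merging 4.8–5.2%. Merging lost 1.1 to 2.3 points of power with weakly prognostic strata. With strongly prognostic strata the change ran from a loss of 0.6 to a gain of about 5 points.

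**5. Bias in a single data set.** Take n = 42, strata of 17, 17, 5 and 3, with the three subjects of the last stratum all on placebo, the others evenly split and no true effect. With strongly prognostic stratum rates of 65, 45, 30 and 15%:

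- Active mean = (8.5 × 65 + 8.5 × 45 + 2.5 × 30)/19.5 = 51.8%.
- Placebo mean = (1010 + 3 × 15)/22.5 = 46.9%.
- Spurious difference = 4.9 points.

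With weak rates of 50, 45, 42 and 38% it is 46.8 − 45.6 = 1.2 points. Merging reduces these to 1.4 and 0.4 points.

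**The case for a change.** The strongest case for a change is that the text permits two readings, that the sponsor itself chose both factors for randomisation and for the main test, and that a single sentence in 9.6 would settle the matter. BSA also has a visible place in the trial, through the rationale and the enrolment quota, so readers will look at that subgroup. In a small subgroup that meets the rule, an unlucky stratum can shift the unadjusted estimate by up to about 5 points in the example above.

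What stands is that 9.6 is silent and that a clarifying clause would do no harm. The rest is weaker.

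- **The test is named.** Section 9.6 falls under 9.0, and 9.1 prescribes CMH for categorical endpoints.
- **The competing reading is strained.** It treats as empty strata that cannot exist once the subgroup is defined. Within one ppIGA level, ppIGA is a constant and only BSA forms strata. The Appendix E code was not written for this question and settles nothing either way.
- **The fallback has a rationale.** A zero-weight stratum contributes none of its subjects to the estimate. The unadjusted comparison keeps every randomised subject, in line with the ITT principle in 9.1.
- **Merging is not clearly better.** It costs power when the factors are weak and its order is arbitrary. Its first step has no meaning inside a BSA subgroup, where no second BSA stratum exists. If everything is merged in the end, it becomes the unadjusted test already in the SAP.

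**Conclusion.** No change follows. The fallback in 9.1 is fixed in advance and valid, and the choice between it and merging strata is a fair trade-off with no consistent winner. The silence in 9.6 is a missing detail that an analyst would fill sensibly by stratifying on the other factor within ppIGA and BSA subgroups.

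If the word-for-word reading were followed, the test would be slightly conservative. The loss in a subgroup of 84 is 0 to 1.2 points of power for placebo gaps of 6 to 20 points between levels, and 4.8 points only for an assumed 40-point gap. No subgroup was powered, no subgroup hypothesis is stated, and both the subgroup results and the DLQI endpoint lie outside the hierarchy.

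The primary test has at most about a 0.2% chance of meeting the rule if 20% or more of subjects are severe. If only 10% are severe, the chance is 0.8–1.8% with blocks of 4 and up to 7.7% with simple 1:1 assignment. The conclusion rests on the assumed severity mix, allocation scheme and prognostic strengths, but no value in these ranges alters a confirmatory claim through the subgroup analyses.
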